#### 14.3 Pre-existing Medical Conditions

Pre-existing medical conditions or symptoms reported prior to device implantation are to be recorded as history and not to be recorded as AEs (e.g., History of Asthma or existing osteoarthritis in contralateral knee would be recorded on the Subject History eCRF). In the event there is an

CONFIDENTIAL Page 35 of 53
Version Date: May 7, 2018

DePuy Synthes / Actis® Total Hip System
Protocol #14014 / Version B

exacerbation of the pre-existing medical condition or symptoms, related to the device or procedure, an AE must be reported.

#### 14.4 Minimization of Risks

The Sponsor will further minimize the identified and/or emergent risks throughout the study, by reviewing the reported complications and adverse effects. Device related adverse events will be reviewed and reported to the FDA as part of the Medical Device Reporting (MDR) requirements (http://www.fda.gov/cdrh/mdr/). Based upon an evaluation of such events, the Sponsor may either amend the investigational plan or terminate the investigation to protect the rights, safety and welfare of the study Subjects. Investigators will be provided periodic reports of all adverse events.

Should an IRB/REB/EC decide to suspend or withdraw its approval for a PI to conduct the study at that institution, based on unacceptable risks to the study Subjects, the study Sponsor will notify all reviewing IRB/REB/ECs, and PIs of this action. To further minimize risks, any new information obtained during the course of the study relating to unanticipated adverse findings will be provided to all Subjects, PIs, and IRB/REB/ECs.

The study has been designed to minimize the number of Subjects, yet provide sufficient numbers of Subjects for valid scientific analysis of the compiled study data. The study design, the procedures for oversight and the documentation, reporting and evaluation of the results from its surgical use will further control risks.

## 14.5 Table 9 Revisions and Reoperations

A "**revision**" is defined as a surgical procedure of the affected study hip where any Actis® Total Hip System component for any reason is removed. A revision algorithm specifically for this study is as follows:

Table 9 Revisions and Reoperations			
Component(s)	eCRFs to be completed	Actions	
revised/removed			
All 4 components removed:	AE eCRF	Subject is revised and	
femoral stem and head,	End of Study eCRF	withdrawn from the study	
acetabular cup and liner			
Exchange of only the	AE eCRF	Subject is categorized as	
polyethylene acetabular liner		revised but not withdrawn from	
(only poly liners are allowed in		study	
the study)		Continue to follow through the	
		2-year endpoint	
Removal of only the femoral	AE eCRF	Subject is revised and	
stem and head (acetabular cup	End of Study eCRF	withdrawn from the study	
and liner remain in place)			
Removal of only the acetabular	AE eCRF	Subject is categorized as	
cup and liner (femoral stem		revised but not withdrawn from	
and head remain in place)		study	
		Continue to follow through the	
		2-year endpoint	

A "re-operation" is defined as any surgical procedure of the affected study hip in which **NO THA** components are removed. These subjects are not to be withdrawn. An **AE eCRF must be** completed (e.g., reoperation could occur to treat an infection).

All removed components are subject to further evaluation. If the implant is known to be available, the Sponsor will encourage the Investigator to preserve the prosthesis alone. In the event of a death, the excised hip joint with the implant in place should be provided to the Sponsor if possible. Please contact the Sponsor for details should a retrieved study implant become available.

# 15 INFORMED PATIENT CONSENT (IPC) PROCESS

In compliance with ISO 14155 and 21CFR50, no Subject shall be enrolled in an investigation without provision of adequate informed consent. The Principal Investigator is responsible for ensuring that no Subject is included in the study without adequate informed consent being provided. Failure to obtain and properly document this process is in violation of ISO 14155, the Declaration of Helsinki, and this study protocol.

CONFIDENTIAL Page 37 of 53
Version Date: May 7, 2018

DePuy Synthes / Actis® Total Hip System
Protocol #14014 / Version B

All Informed Patient Consent (IPC) documents must have favorable opinion of the IRB/REB/EC. Many institutions request modification of the IPC to satisfy specific institutional requirements. The use of a modified or unique IPC is permitted provided that all the requirements of ISO 14155 are met and the document is approved before use by the Sponsor.

Subjects who agree to participate in the study will complete an IRB/REB/EC approved IPC document that documents his or her willingness to take part in this study. Each potential Subject will have the nature and the purpose of this study explained to him or her by the Principal Investigator (PI) or another delegated member of the investigative team at the study Site. The PI or designee will explain the following features of the study to the patient thoroughly and will offer to answer any questions the patient may have.

- The purpose of the study
- The potential risks or adverse events that are posed by their treatment
- The potential risks or adverse events related to study participation
- Possibility of failure and the need for subsequent treatment(s)
- Alternative procedures/treatments available to the Subject
- Requirements of the study follow-up visits
- All the Subject's rights as a participant in the clinical investigation
- The plan to perform retrieval analysis in the event of an explanted device
- A modest payment may be provided to cover Subject travel expenditures associated with study participation up to 2 years postoperatively
- Voluntary participation in the Patient Activity Tracking portion of the study, and the details associated with this portion of the study.

Consent must be given by the Subject, or by a Legally Authorized Representative as applicable, and documented on an Informed Patient Consent Document in the primary language of the Subject. A copy of the IPC is to be provided to the Subject. An IPC must be obtained for all Subjects prior to the Subject completing any study-specific assessments or procedures that are not standard of care. A study Subject is considered enrolled in the study once they have signed the IPC.

CONFIDENTIAL Page 38 of 53
Version Date: May 7, 2018

DePuy Synthes / Actis® Total Hip System
Protocol #14014 / Version B

Obtaining Consent Day of Surgery: If the IPC document signatures are acquired on the day of surgery a **time stamp** on the signature page is required to support consent was obtained from the study Subject prior to any treatment related and/or mood-altering medications being administered.

No dates should be pre-populated, or completed by someone other than the person providing the signature.

Subjects will be made aware that their personal data will be collected and processed in accordance with data protection legislation including Health Insurance Portability and Accountability Act of 1996 (HIPAA - refer to **Section 5, Table 3, Definition of Terms**). The release of Personal Health Information (PHI) for the purpose of this clinical investigation will be included in the informed patient consent. Results from this clinical investigation may be published, however, subject confidentiality will be maintained at all times and it will not be possible to identify them from any data presented.

#### 16 STATISTICAL METHODOLOGY

Statistical analysis will be performed using SAS® (SAS Institute Inc., [name]) software version 9.3 or higher. Any further software that may be necessary will be described in the final study report.

# 16.1 Study Design

The study design is a prospective, uncontrolled, non-randomized, multicenter study.

A minimum of 255 Subjects that includes a minimum cohort of 225 Primary THA and a cohort of a minimum of 30 hemi-hip arthroplasty Subjects, will be prospectively enrolled into the study. All Subjects will be seen for a preoperative clinic visit at the time of consent, and evaluated at the time of surgery, 6 weeks, 3 months, minimum 1 year, and minimum 2 years postoperatively.

# **16.2** Treatment Assignment

The Actis® Total Hip System, specifically the medial collared DUOFIX® hip stem, is the only device of interest in the study; there will be no control group. Two cohorts of Subjects will be enrolled:

- Subjects who receive a primary THA
- Subjects who undergo a primary hemi-hip arthroplasty.

# 16.3 Levels of Significance

There are no pre-specified hypotheses, and all analyses are exploratory. Confidence intervals and p-values may be provided to facilitate clinical judgement. Unless otherwise stated, p-values will be 2-sided and confidence intervals will be 2-sided 95% confidence intervals with no adjustments for multiplicity.

CONFIDENTIAL Page 39 of 53
Version Date: May 7, 2018

DePuy Synthes / Actis® Total Hip System
Protocol #14014 / Version B

#### 16.4 Interval Windows

See Section 6 Subject Management Study Schedule above.

# 16.5 Handling of Missing Data

. Only actual subject data which is collected will be utilized in analyses.

# 16.6 Primary and Secondary Endpoints

See Sections 10.2 and 10.3

### 16.7 Hypotheses

This is not a hypothesis driven study.

[figure not shown]
### 16.8 Analysis Sets

- This study will have 3 analysis sets which will be determined for both THA and hemi-hip Subjects as defined below and illustrated in the Data Flow Diagram: Enrolled Set is defined as all cases consented to participate in this study. The Enrolled Set will be used for the summary of disposition.
- Safety Set is defined as all cases that received the Actis® Total Hip System. The Safety Set will be used to summarize demographic characteristics, adverse events and survivorship;
- Per Protocol Set is defined as all Safety Set subjects without major protocol violations. The Per Protocol Set will be used for the summary of primary, secondary and tertiary endpoints.

CONFIDENTIAL Page 40 of 53
Version Date: May 7, 2018

DePuy Synthes / Actis® Total Hip System
Protocol #14014 / Version B

Figure 16-1: Analysis Set Flowchart

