Primary, Secondary and Tertiary Endpoints:	
 
Primary endpoint:     Harris Hip Score at minimum 2-years postoperatively.
 
Secondary endpoints: 
 
Harris Hip score at 3-months and 1-year
 
Radiographic evaluation at 2-years postoperatively, inclusive of leg length discrepancy
 
Type and frequency of device and procedure related AEs through 2-years postoperatively
 
Device survivorship at 2-years postoperatively
 
 
 
Tertiary endpoints: 
 
Change in Subject Outcomes (i.e., FJS-12, HOOS and Subject Hip Evaluation) will be measured and compared from preoperative to 6-weeks, 3-months, minimum 1-year and minimum 2-years.
 
Study Sites will be given the opportunity to participate in a non-required parallel activity (to collect tertiary outcomes) of this study, specifically, "Patient Activity Tracking".
 
At the participating study sites, Subjects choosing to participate in Patient Activity Tracking will wear a device that looks somewhat like a wrist watch. The Patient Activity Tracking device will link via a downloaded mobile application (app) (i.e., ActiTrakTM) to the Subject's smartphone (i.e., iPhone or Android phone) or to a Sponsor provided Android tablet. Any Sponsor provided Android tablet will be for study use only in order to provide pre-populated passive and actively reported Subject activities such as Pain, Location of Pain, Mood/Emotion, Activities of Daily Living, and Range of Motion from the time of consent preoperatively through 3 months postoperatively. After surgery, there will be question about Subject Satisfaction periodically. Any Sponsor provided Android tablet will be returned to the Sponsor at the 3-month follow-up interval or at any premature study termination after consent and enrollment.
 
 
 
	

Table 2 Study Summary	
Title:	Actis® Total Hip System 2-Year Follow-up
Procedure Schedule:	Subjects will be seen at the following intervals: preoperative, operative, 6-weeks, 3-months, minimum 1-year, and minimum 2-years postoperatively.
Safety:	Only device or procedure related adverse events (AEs) for enrolled Subjects are to be reported.

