## 12.3 Actions for Screen Failure Subjects

Subjects can be a screen failure prior to surgery (*e.g.*, withdraw of consent) or be considered a screen failure when withdrawn intra-operatively; intra-operative screen failure could be due to the Subject requiring a non-study implant. **Table 5** below provides further examples of screen failures and required actions.

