# 12.4 Table 5 Actions for Screen Failure Subjects

	Table 5 Actions for Screen Failure Subjects (Based on the definition of an Enrolled Subject in Section 9)					
Screen Failure Type	Screening/ Enrollment Log?	Data submitted To EDC?	Enrolled Subject?	Example	Action	
Pre- operative screen failure	Yes	Yes	Yes	Subject signed IPC, meeting the definition of enrolled, but has withdrawn consent before surgery or no longer meets inclusion/exclusion criteria at time of surgery	Document on Screening & Enrollment Log as Preoperative Screen Failure  Complete & enter Preoperative eCRFs if data was collected: DM, HH, HE, HOOS and DS	

CONFIDENTIAL Page 25 of 53
Version Date: May 7, 2018

DePuy Synthes / Actis® Total Hip System
Protocol #14014 / Version B

Intra- operative screen failure	Yes	Yes	Yes	Subject signed IPC, meeting the definition of enrolled, but it was determined during surgery that the Subject would not have the Actis® Total Hip System implanted	Document on Screening & Enrollment Log as Intra- operative Screen Failure  Complete & enter Preoperative & Operative eCRFs if data was collected: DM, HH, HE, HOOS, PA and DS
--	-----	-----	-----	--	---

Overall, the number of study Subjects implanted with the Actis® Total Hip System, across all study sites, must meet the total sample size of 255 Subjects that includes a minimum of 225 Primary THA Subjects and a cohort of a minimum of 30 hemi-hip arthroplasty Subjects. Meaning, you can replace Subjects who have screen failed prior to implantation.

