#### 13 ADVERSE EVENTS (AES)

An adverse event (AE) is defined as an untoward medical occurrence, unintended disease or injury, or untoward clinical signs (or change or worsening of a pre-existing medical condition) in a patient, which may or may not have an association with the device. In addition, an adverse device effect is defined as "any untoward and unintended response to a medical device". Further types of AEs and definitions are in **Table 7** below. AEs are reported beginning from when the informed consent is signed until Subject participation has ended (study completed or consent withdrawn. This protocol requires each site to report AEs to their respective IRB/REC, EC, per their IRB/REB/EC's respective requirements. Device related AEs will be reviewed by DePuy Synthes and reported, if applicable, to the appropriate regulatory body.

Study Sites have two (2) weeks from when they become aware of device and /or procedure related AEs to inform the Sponsor via the AE eCRF.

For this study, only the AEs related to the study devices (excluding the Patient Activity Tracking devices) or the procedure are to be reported (please refer to Figure 13.1). The determination whether the AE was related to the device or procedure will be based upon whether a causal relationship between the device or procedure and the AE is at least a reasonable possibility, *i.e.*, the relationship cannot be ruled out. A causal relationship cannot be ruled out if, in the medical judgment of the Investigator, the effect follows a reasonable temporal association with the use of the device and/or is confirmed by the improvement of the effect upon discontinuation of the clinical use of the device, and/or the effect is not reasonably explained by the Subject's clinical state.

A record of each device or procedure related AE, including details of the nature, onset, duration, severity, relationship to the device, relationship to the operative procedure and outcome, will be made on an AE eCRF. Subjects must be questioned about any new or changed AEs at each subsequent follow-up visit, whether scheduled or not.

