#### 17 DATA MANAGEMENT

# 17.1 Data Management for Subject Operative Details and Follow-up Evaluations

Electronic Case Report Forms (eCRFs) entered into an electronic data (EDC) system will be used to collect all Subject data once a Subject is enrolled in the study. Study sites will be asked to enter Subject data into the eCRFs via the EDC web based database portal promptly after each study visit.

The patient-reported outcome measures (*i.e.*, FJS-12, HOOS and Hip Evaluation) will be recorded on paper-based questionnaires. The data will then be entered into the respective eCRF within the EDC system by the PI or designee. The patient-reported outcomes measures captured on paper-based questionnaires must be stored in the Subject's medical notes, as these are the source document. Any errors on paper-based questionnaires should be crossed out with a single stroke, initialed and dated by the Subject; a study site must not alter any data entered on the paper-based questionnaires. Typing correction fluid must not be used. The PI will retain one copy of each completed paper-based

CONFIDENTIAL Page 44 of 53
Version Date: May 7, 2018

DePuy Synthes / Actis® Total Hip System
Protocol #14014 / Version B

questionnaires (e.g., HOOS) in the medical notes and another copy will be kept in the site study file (e.g., individual study Subject binder or Subject specific tab if contained within a single binder).

For all Subjects, detailed information related to the primary diagnosis, anesthesia type and time, if a specific kind of fracture table (*e.g.*, HANA Table) was utilized, and surgical exposure (*e.g.*, anterior approach), and other surgical variables will be recorded on the Operative Details eCRF. Any occurrence of an operative complication must be recorded on the AE eCRF. An intra-operative device or procedure related complication is defined as a complication that occurs from the start of anesthesia to when the Subject returns to their room. Please complete a separate AE eCRF for each intra-operative complication. Labels for each device or component used during the procedure must be recorded on Device Log eCRF.

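### Operations started but ended without Actis fall outside the planned summary of intra-operative adverse events, and Table 5 does not list the AE form for them

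*Combined protocol and SAP*

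**What the plan says.** **Analysis sets.** Section 16.8 names three sets. The Safety Set carries demographics, AEs and survivorship, and its definition begins "Safety Set is defined as all cases that received the Actis" system. The Per Protocol Set is the part of the Safety Set without major violations, and it carries the primary, secondary and tertiary endpoints. The third set has one stated use: "The Enrolled Set will be used for the summary of disposition".

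**The cases at issue.** Section 12.3 foresees withdrawal during surgery: "intra-operative screen failure could be due to the Subject requiring a non-study implant". Table 5 counts these persons as enrolled, and the text below it allows replacement of subjects who screen-failed before implantation. For the intra-operative row it instructs: "Complete & enter Preoperative & Operative eCRFs if data was collected: DM, HH, HE, HOOS, PA and DS".

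**AE recording.** The Safety row of Table 2 states: "Only device or procedure related adverse events (AEs) for enrolled Subjects are to be reported". Section 13 states: "AEs are reported beginning from when the informed consent is signed until Subject participation has ended". Section 17.1 states: "Any occurrence of an operative complication must be recorded on the AE eCRF". It defines an intra-operative device or procedure related complication as "a complication that occurs from the start of anesthesia to when the Subject returns to their room". The section 6 schedule marks the AE form at the operative visit.

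**The endpoint.** Type and frequency of device and procedure related AEs through two years is a secondary endpoint (Table 2; section 10.3 lists AEs without the qualifier). Section 16.12 plans a table and a listing, and names no population for the listing.

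**The concern.** Membership of the Safety Set is settled during surgery, when subjects are already at risk of procedure-related events. Section 13 lists acetabular perforation, femoral perforation or fracture, and trochanteric fracture among intra-operative events, and these can happen before a stem is finally seated. For such events the natural denominator is procedures started. The plan uses procedures completed with Actis, so a selection made on the operating table decides who counts.

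The form list adds a practical risk. A site that follows Table 5 literally for an intra-operative screen failure would submit neither an AE form nor an Operative Details form. Section 18 does not require on-site interim monitoring, so the gap could go unnoticed. What is at stake is the completeness of one descriptive safety rate.

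**Working it through.** **1. Who is counted.** The plan gives no AE rate and no count of intra-operative screen failures, so there is no figure of its own to reproduce on this point. The check starts from the definitions.

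- Operated but not implanted: not in the Safety Set, which requires receipt of Actis.
- Not in the Per Protocol Set either, because it is a subset of the Safety Set. Whether AEs are read as Safety Set output or as a secondary endpoint, the same persons are missing.
- In the Enrolled Set, but that set is named only for disposition.

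Figure 16-1 is not shown in the text available, so it could not be compared with these definitions.

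**2. Whether the AEs are recorded.** Table 2, the section 6 schedule, section 13 and section 17.1 all lead to an AE form. Table 5's intra-operative row asks for operative forms but names only DM, HH, HE, HOOS, PA and DS. It leaves out the AE, Operative Details and Device Log forms. Nothing in Table 5 forbids them, so the defect is an incomplete list.

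**3. Direction.** Let x of 225 implanted THA subjects have the event (225 is the planned THA minimum), and a of k non-implanted subjects.

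- Reported rate: x/225. Rate for all procedures started: (x + a)/(225 + k).
- The second exceeds the first when 225(x + a) > x(225 + k), that is, when a/k > x/225.
- The reported rate is therefore too low if the event is more frequent in non-implanted cases, unchanged if equally frequent, and too high if less frequent.

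**4. Size, for an intra-operative event only.** All event and abandonment counts are assumptions. If 1% to 3% of attempts end without Actis, 225 implanted cases correspond to 225/0.99 = 227.3 to 225/0.97 = 232.0 attempts, so k is about 2 to 7. Take x = 2. Intervals are exact binomial, the method that section 16.10 plans for percentages.

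| k | a | Rate, procedures started | 95% CI |
|---|---|---|---|
| 0 (as reported) | 0 | 2/225 = 0.89% | 0.11 to 3.17% |
| 3 | 0 | 2/228 = 0.88% | 0.11 to 3.13% |
| 3 | 1 | 3/228 = 1.32% | 0.27 to 3.80% |
| 3 | 3 | 5/228 = 2.19% | 0.72 to 5.04% |
| 7 | 7 | 9/232 = 3.88% | 1.79 to 7.24% |

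For k = 3 the shift runs from -0.01 to +1.30 percentage points. The break-even at k = 3 is a = 3 × 2/225 = 0.03, so a single event among the three already puts the reported rate on the low side. The top of the range needs an event in every abandoned operation. All the intervals overlap.

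**The case against.** **The Safety Set is a deliberate and coherent choice.** The study is about the performance and safety of Actis, and Table 5 counts the sample by implanted subjects. This stands for device-related AEs and survivorship, and the set should stay for the planned AE summary. It does not answer the point for procedure-related events during the operation, where the risk precedes implantation.

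**The documents do not really conflict on recording.** A reader might infer that they do, because section 9.1 defines a Subject as a recipient of the product and Table 4 describes the AE form for AEs after surgery. That reading is not supported. Section 9.1 goes on to say that a person may be called a patient before consent, which fits Subject status from consent. The schedule marks the AE form at the operative visit, and section 17.1 is mandatory. Table 5's list is qualified by whether data were collected, and its pre-operative row omits the AE form too, so it may simply not deal with event-driven forms. What stands is that the row for exactly these cases is incomplete and can mislead a site.

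**No bias has been shown.** This is correct. The number of cases may be zero, the example in section 12.3 mentions no complication, and the direction depends on unknown counts. The AE listing might include these cases, since its population is not stated. SAE and UADE notification (Tables 7 and 10) is not limited to the Safety Set.

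**Conclusion.** The point holds in a limited form. By definition, operations started but ended without Actis are absent from the planned intra-operative AE rate, and the form list for these cases is incomplete. Under the assumed counts (x = 2, k = 3) the rate moves from 0.89% to between 0.88% and 2.19%.

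Two stronger readings are tempting and not supported. One is that the reported rate is biased downward: that requires a/k > x/225, and the documents give neither the number of such cases nor their events. The other is that the overall two-year AE rate is affected in the same way. Non-implanted subjects leave the study with an End of Study form and have no two-year follow-up, so pooling them into a two-year rate would mix unequal exposure. Only the intra-operative window supports the comparison.

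Severity is minor. Section 16.3 calls all analyses exploratory, no decision threshold rests on this rate, and neither the sample size nor the Harris Hip Score analysis changes.

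**What to change.** 1. Keep the Safety Set for the planned AE summary, device-related AEs and survivorship.
2. Add to section 16.12 one supplementary table and listing of intra-operative device or procedure related complications. Limit it to the section 17.1 window, from start of anesthesia until return to the room, and include all enrolled subjects whose procedure was started.
3. In the Enrolled Set disposition, report the number operated on but not implanted, with reasons. The reasons are already collected through the screening log (section 9.2), the End of Study form (Table 4) and the withdrawal documentation (section 22.2). If the number is zero, say so.
4. Reconcile Table 5's intra-operative row with section 17.1 by adding the AE, Operative Details and Device Log forms. Cite Operative Details by name, because its code is SG in section 6 and OP in Table 4.

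**Cost.** SAP wording, one table with its listing, and one row of Table 5. The 225 THA subjects were reached on June 5, 2017 (section 10.6), before this version of May 7, 2018. For THA the change therefore means retrospective queries on any such cases, and some details may not be recoverable. The supplementary rate may look slightly less favourable than the Safety Set rate.

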#### 12.6 Table 6 Actions for Postoperative Withdrawal

Table 6 Actions for Postoperative Withdrawal					
Example	Actions	Follow -up			
Subject	Document Subject's request for withdrawal from				
withdraws	

the study in the source

Complete End of Study/Withdrawal eCRF

	Do not continue			
consent	Update Screen/Enrollment Log				
	Document in source				
D 41	Complete Adverse Event eCRF	Do not			
Death	Complete End of Study/Withdrawal eCRF	continue			
	Update Screen/Enrollment Log				
	See Section 14.5, Table 9 Revisions and	Do not continue if the			
Revision	Reoperations	femoral stem has been			
	Acopei ations	removed or revised.			

CONFIDENTIAL Page 26 of 53
Version Date: May 7, 2018

DePuy Synthes / Actis® Total Hip System
Protocol #14014 / Version B

	Please continue to follow
	if the femoral component
	has not been removed or
	revised

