# 16.9 Sample Size Justification

The primary endpoint in this study is the Harris Hip Score at minimum 2-year postoperative. It is anticipated that this primary outcome measurement will be obtained on approximately 200 primary THA Subjects due to anticipated attrition. The standard deviation in this outcome will be approximately 10 points (based on historical hip studies). It is therefore anticipated that the margin of error on the mean Harris Hip Score estimate at minimum 2-years postoperatively will be approximately 1.4 points. The study team believes this margin of error is sufficient for this 2-year outcomes and follow-up study. A sample size of N=30 hemi-hip arthroplasty procedures was established as a feasible number.

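### The 2-year Harris Hip Score mean is summarised only in Per Protocol subjects with a collected score; no summary in all implanted subjects and no missing-data sensitivity analysis is planned

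*Combined protocol and SAP*

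**What the plan says.** - **Analysis set.** Section 16.8: "The Per Protocol Set will be used for the summary of primary, secondary and tertiary endpoints". That set is the Safety Set (all who received the device) minus major protocol violators. The Safety Set itself is assigned demographics, adverse events and survivorship, but not HHS.
- **Missing data.** Section 16.5: "Only actual subject data which is collected will be utilized in analyses".
- **Stem removal.** Table 6 (section 12.6) stops follow-up when the "femoral stem has been" removed or revised. Table 9 (section 14.5) has the same outcome when the stem is removed: "Subject is revised and" withdrawn. Under both tables, subjects who keep their stem stay in follow-up.
- **Expected loss.** Section 12.4 says the number implanted "must meet the total sample size of 255 Subjects that includes a minimum of 225 Primary THA Subjects", and only subjects who fail screening before implantation may be replaced. Section 16.9: "It is anticipated that this primary outcome measurement will be obtained on approximately 200 primary THA Subjects due to anticipated attrition".
- **Planned HHS output.** Section 16.11 gives descriptive statistics and a t-based 95% interval, combined and by cohort; section 16.10 adds results by site. Sections 16.8 to 16.14 contain no HHS summary in all implanted subjects and no missing-data sensitivity analysis.
- **Framing.** Section 16.2: "there will be no control group". Section 16.3: "There are no pre-specified hypotheses, and all analyses are exploratory".

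**The concern.** The primary objective (section 10.1) is performance in a series of implanted hips. Two separate rules narrow the HHS mean to part of that series. The Per Protocol restriction removes major violators even when they have a score. Withdrawal together with the collected-data rule removes stem-revised subjects, deaths and other dropouts.

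If those left out would have scored lower, the mean is too high as a description of everyone implanted, and no planned analysis would show by how much. With no comparator, the absolute mean is itself the result, so a selection effect cannot cancel between arms. The only precision statement is the 1.4-point margin of section 16.9, which covers sampling error and not selection.

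**Working it through.** **Inputs from the documents.** SD 10 and about 200 THA scores (section 16.9); at least 225 implanted THA subjects (section 12.4); 2-sided 95% intervals (section 16.3). **Assumed, because the documents are silent:** every HHS deficit, the revision rates, the Per Protocol exclusion rates and the number of deaths.

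**1. The plan's margin.** SE = 10/√200 = 0.707. With t(199) = 1.972, the margin is 1.972 × 0.707 = 1.394. The stated 1.4 reproduces.

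**2. Attrition.** The missing fraction is f = 25/225 = 11.1%, from all causes; the plan does not split it by reason. If missing subjects average d points lower than observed ones, the observed mean exceeds the all-implanted mean by f × d.

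| Assumed d | f × d |
|---|---|
| 5 | 0.56 |
| 10 | 1.11 |
| 15 | 1.67 |

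The bias equals the margin at d = 1.394/0.1111 = 12.5 points. The break-even moves with the missing fraction:

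- 210 scores: f = 15/225 = 6.7%, margin 1.360, break-even 20.4.
- 190 scores: f = 35/225 = 15.6%, margin 1.431, break-even 9.2.
- 200 scores with 5 assumed deaths set aside: f = 20/220 = 9.1%, break-even 1.394/0.0909 = 15.3.

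**3. Per Protocol exclusion alone.** Bias = p × d, where p is the share of scored subjects excluded and d is 5 to 10 points.

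| p | n left | Margin | Bias |
|---|---|---|---|
| 2% | 196 | 1.41 | 0.10–0.20 |
| 5% | 190 | 1.43 | 0.25–0.50 |
| 10% | 180 | 1.47 | 0.50–1.00 |

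All are below the margin.

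**4. Stem revision alone.** Bias = rate × d. The range runs from 1% × 30 = 0.3 to 3% × 40 = 1.2, below the margin. Reaching it takes a rate of 4.6% at 30 points or 3.5% at 40 points.

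**5. What a model on earlier scores could recover.** A simulation used 225 subjects, 4,000 replicates, mean 90, SD 10, a 1-year to 2-year correlation of 0.7 and 11.1% missing. It regressed 2-year on 1-year HHS in completers. This is simpler than a repeated-measures model on all earlier visits, so it is only indicative.

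- Dropout driven by the 1-year score: completer bias of 0.38 to 0.70 falls to about 0.
- Dropout driven by the 2-year score: completer bias of 0.54 to 1.00 falls only to 0.28 to 0.53.

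Such a model does not account for stem failure. For example, an assumed 2% revision at a 35-point deficit contributes 0.02 × 35 = 0.7 points, which it leaves in place.

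**The case against.** The strongest reply is that nothing formal depends on this. The study is exploratory, with no hypothesis or threshold. That stands, and it limits the weight of the point.

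Much is also reported elsewhere. Any-component and stem-specific Kaplan-Meier analyses are planned for THA and run in the Safety Set. Disposition is summarised in the Enrolled Set, withdrawal reasons are collected, n accompanies each HHS mean, and data up to withdrawal are kept (section 12.5). A reader could work out the missing fraction and apply f × d. This stands too, but none of it enters the HHS mean or shows its sensitivity, and data kept up to withdrawal supply no 2-year score.

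Loss may be smaller than planned. The 2-year window runs from day 669 to day 1763 (section 6), section 20.1 requires continued contact attempts, and section 9.3 retains subjects operated on by another approach. Major violations are not defined in the text and Figure 16-1 is not shown, so Per Protocol loss cannot be computed. Section 16.5 begins with a stray full stop, so earlier text there may be lost; the absence of a sensitivity analysis is firmer for sections 16.8 to 16.14.

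Reporting function beside separate survivorship is also a defensible choice, since a score after stem removal describes a different hip. For that reason an assigned low score or a composite is a preference, not a correction.

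A reader might infer that the HHS mean will be materially inflated, or that leaving out revised or protocol-violating subjects alone would swamp the stated precision. The documents do not support either reading. They give no HHS for the missing subjects, and each mechanism alone stays below the margin over the ranges tried.

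**Conclusion.** The point holds as a gap in the planned reporting of the primary endpoint, not as a demonstrated bias. Only the 11.1% planned loss and the 1.4-point margin rest on the documents; every deficit is assumed. At the planned loss, missing subjects would have to average about 12.5 points lower, 1.25 times the planning SD, for the bias to equal the margin. With 210 or 190 scores that figure becomes 20.4 or 9.2. A smaller bias is still not covered by the interval, and the planned analyses would not reveal it. The change is worth making because it is cheap and concerns the study's main estimate.

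Two neighbouring inconsistencies need reconciling but are separate. Section 10.2 places the primary analysis in THA subjects while section 16.11 combines both cohorts; the calculations here are for THA only. Section 12.5 lists acetabular revision as a withdrawal, while Tables 6 and 9 continue follow-up when the stem stays in place.

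**What to change.** 1. In sections 16.8 and 16.11, summarise 2-year HHS in the Safety Set and keep the Per Protocol summary as supportive. This restores violators who have a score; it does not replace scores never obtained.
2. Add a supportive repeated-measures estimate using the HHS already collected preoperatively and at 6 weeks, 3 months and 1 year. State that it addresses only dropout explained by observed scores and does not account for stem failure.
3. Beside the HHS mean, report how many subjects lack a 2-year score, by reason (stem revision, death, other). Add a short descriptive table, without a decision threshold, of the mean over a prespecified range of deficits for missing living subjects. Give deceased subjects no imputed score. Section 16.5 needs a sentence permitting this table.
4. Optionally, show stem-revised subjects with an assigned low score or through a composite of HHS and no stem revision, justified in advance.

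Apply this to the THA cohort and to whichever population is primary once sections 10.2 and 16.11 agree.

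The cost is SAP wording and modest programming, with no new data. The assumed deficits must be justified beforehand, and the headline mean may be slightly less favourable.
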